## 3.2 Study Population

The study population consists of ipilimumab naïve subjects with unresectable Stage III or Stage IV melanoma who satisfy the inclusion and exclusion criteria.

For entry into the study, the following criteria MUST be met. No exceptions will be granted.

### 3.2.1 Inclusion Criteria

#### 1) Signed Written Informed Consent

The signed informed consent form prior to the performance of any study related procedures that are not considered part of standard of care.

#### 2) Target Population

- a) Subjects who are ipilimumab naïve with progressive unresectable Stage III or Stage IV melanoma who are either treatment naïve or may have been treated with up to 3 prior treatments for melanoma (eg, chemotherapy, biologic or targeted therapy or IL-2).
- b) Histologic or cytologic confirmation of stage III or stage IV melanoma
- c) Measurable disease at baseline as assessed by CT and/or MRI
- d) Eastern Cooperative Oncology Group (ECOG) Performance Status of 0 or 1
- e) Screening laboratory values must meet the following criteria
  - i) WBCs  $\geq 2000/\mu\text{L}$
  - ii) Neutrophils  $\geq 1500/\mu\text{L}$
  - iii) Platelets  $\geq 100 \times 10^3/\mu\text{L}$
  - iv) Hemoglobin  $\geq 9.0 \text{ g/dL}$
  - v) Creatinine Serum creatinine  $\leq 1.5 \times \text{ULN}$  or creatinine clearance  $> 40 \text{ mL/minute}$  (using Cockcroft/Gault formula)
  - vi) AST  $\leq 3 \times \text{ULN}$
  - vii) ALT  $\leq 3 \times \text{ULN}$
  - viii) Total Bilirubin  $\leq 1.5 \times \text{ULN}$  (except subjects with Gilbert Syndrome who must have total bilirubin  $< 3.0 \text{ mg/dL}$ )

### **3) Age and Reproductive Status**

Men and women  $\geq 18$  years old

- a) Men and women of childbearing potential (WOCBP) must be using an acceptable method of contraception to avoid pregnancy throughout the study and for at least 12 weeks after the last dose of investigational product in such a manner that the risk of pregnancy is minimized. See Section 3.3.3 for the definition of WOCBP.
- b) Women must have a negative serum pregnancy test (minimum sensitivity 25 IU/L or equivalent units of HCG) within 72 hours prior to the start of investigational product.

### **3.2.2 Exclusion Criteria**

#### **1) Target Disease Exceptions**

- a) Subjects with known or suspected brain metastasis, or brain as the only site of disease are excluded with the following exceptions.
  - i) Subjects with controlled brain metastasis (no radiographic progression at least 4 weeks following radiation and/or surgical treatment, off steroids for at least 4 weeks, and have no new or progressing neurological signs or symptoms) will be allowed.
  - b) Subjects with a history of prior malignancy with the exception of carcinoma in situ of the cervix or other malignancy diagnosed  $> 2$  years ago that has undergone potentially curative therapy with no evidence of disease for the last  $\geq 2$  years and that is deemed by the investigator to be at a low risk of recurrence.

#### **2) Medical History and Concurrent Diseases**

- a) Active autoimmune disease or a history of known or suspected autoimmune disease with the exception of subjects with isolated vitiligo, treated thyroiditis or resolved childhood asthma/atopy.
- b) Known human immunodeficiency virus (HIV), active hepatitis A, or hepatitis B or C infection.
- c) History of any hepatitis (eg, alcohol or non-alcohol steatohepatitis (NASH), drug-related, autoimmune)
- d) Evidence of active infection that requires anti-bacterial, anti-viral, or anti-fungal therapy  $\leq 7$  days prior to initiation of study drug therapy
- e) History of acute diverticulitis, or current chronic diarrhea
- f) Active peptic ulcer disease even if asymptomatic
- g) History of adrenal insufficiency (including subjects using replacement therapy)
- h) Prior organ allograft or allogenic bone marrow transplantation
- i) Uncontrolled or significant cardiovascular disease including, but not limited to, any of the following:
  - i. Myocardial infarction within the past 6 months
  - ii. Uncontrolled angina within the past 6 months
  - iii) Any history of clinically significant ventricular arrhythmias (such as ventricular tachycardia, ventricular fibrillation or Torsades de pointes). Controlled atrial fibrillation by itself is not an exclusion criterion.
  - iv) Baseline QTc interval greater than 500 milliseconds
- j) Baseline toxicities from prior anti-cancer treatments  $> \text{Grade } 1$ .
- k) Inability to be venipunctured and/or tolerate venous access.
- l) Any major surgery within 4 weeks or a diagnostic procedure (eg incision, needle

- biopsy) within 1 day of study drug administration.
- m) Any current or recent (within 3 months) gastrointestinal disease that could potentially impact the ability to swallow and/or absorb study drug (ie, gastrointestinal surgery, malabsorption syndrome).
  - n) Diabetes mellitus uncontrolled by medication.
  - o) Known drug or alcohol abuse.
  - p) Presence of underlying medical condition that in the opinion of the Investigator or Sponsor could adversely affect the ability of the subject to comply with or tolerate study procedures and/or study therapy, or confound the ability to interpret the tolerability of combined administration of panobinostat and ipilimumab in treated subjects.

### 3) Allergies and Adverse Drug Reaction

- a) History of allergy to components of ipilimumab or panobinostat, or known allergy to other antibody therapies.

### 4) Sex and Reproductive Status

- a) WOCBP who are **unwilling or unable** to use an acceptable method to minimize the risk of pregnancy for the entire study period and for at least 12 weeks after the last dose of investigational product.
- b) Women who are pregnant or breastfeeding.
- c) Women with a positive pregnancy test on enrollment or prior to investigational product administration.
- d) Sexually active fertile men not using effective birth control if their partners are WOCBP.

### 5) Prohibited Prior Treatments and/or Therapies

- a) Exposure to any investigational drug within 4 weeks of study drug administration.
- b) Any anti-cancer therapy (eg, chemotherapy, biologics, radiotherapy, or hormonal treatment) within 4 weeks or at least 5 half-lives (whichever is longer) of study drug administration.
- c) Prior therapy with an anti-CTLA4 antibody or an HDAC inhibitor
- d) Concurrent chemotherapy, hormonal therapy, immunotherapy regimens, or radiation therapy, standard or investigational.

### 6) Other Exclusion Criteria

- a) Prisoners or subjects who are involuntarily incarcerated
- b) Subjects who are compulsorily detained for treatment of either a psychiatric or physical (eg, infectious disease) illness

#### 3.2.3 Women of Childbearing Potential

Women of childbearing potential include any female who has experienced menarche and who has not undergone successful surgical sterilization (hysterectomy, bilateral tubal ligation, or bilateral oophorectomy) or is not postmenopausal. Post menopause is defined as:

- Amenorrhea  $\geq 12$  consecutive months without another cause and a documented serum follicle stimulating hormone (FSH) level  $>35$  mIU/mL
- Women with irregular menstrual periods and a documented serum follicle stimulating hormone (FSH) level  $> 35$  mIU/mL

- Women on hormone replacement therapy (HRT)

Women who are using oral contraceptives, other hormonal contraceptives (vaginal products, skin patches, or implanted or injectable products), or mechanical products such as an intrauterine device or barrier methods (diaphragm, condoms, spermicides) to prevent pregnancy, or are practicing abstinence or where their partner is sterile (eg, vasectomy) should be considered to be of childbearing potential.

### **3.3 Concomitant Treatments**

Medications taken within 4 weeks prior to study drug administration and while on study treatment must be recorded.

#### **3.3.1 Prohibited and/or Restricted Concomitant Treatments**

Restrictions on medications taken prior to enrollment in the study are described above in Section 3.3.2. Use of prescription and over-the counter medications (except medications from categories outlined below) is permitted at the discretion of the Investigator and must be recorded.

Concurrent use of the following medications or drug classes while on study therapy is prohibited. In the setting where eligible subjects are already taking these therapies, they should be switched to and stabilized on alternative medications as clinically indicated, and a minimum wash out interval of 5 half-lives of the prohibited medications should be allowed prior to initiation of study therapy.

- 1) Systemic or inhalational corticosteroids. Ocular use of corticosteroids is permitted as is the transient use of topical corticosteroids over a limited surface area. Replacement corticosteroids may be used up to the equivalent of 10 mg of prednisone daily.
- 2) Other immunosuppressive agents

#### **3.3.2 Other Restrictions and Precautions**

Panobinostat may also interact with and inhibit the metabolizing enzyme cytochrome P450 3A4. Therefore, strong inducers, inhibitors, or substrates of CYP3A4, should be used with caution during the study. Investigators are encouraged to consult the sponsor prior to the use of strong modulators of CYP450 activity. Appendix 2 provides examples of drugs in this category.

### **3.4 Discontinuation of Subjects from Treatment**

Subjects MUST discontinue investigational products (and noninvestigational product at the discretion of the investigator) for any of the following reasons:

- Withdrawal of informed consent (subject's decision to withdraw for any reason)
- Any clinical adverse event (AE), laboratory abnormality or intercurrent illness which, in the opinion of the investigator, indicates that continued participation in the study is not in the best interest of the subject
- Pregnancy (see Section 6.4)
- Loss of ability to freely provide consent through imprisonment or involuntarily incarceration for treatment of either a psychiatric or physical (eg, infectious disease) illness
- Subject's inability to comply with the protocol

- Toxicity requiring discontinuation as outlined in the Guidelines for Dose Modification (Section 4.3.5)

All subjects who discontinue should comply with protocol specified follow-up procedures as outlined in Section 5. The only exception to this requirement is when a subject withdraws consent for all study procedures or loses the ability to consent freely (ie, is imprisoned or involuntarily incarcerated for the treatment of either a psychiatric or physical illness). If a subject was withdrawn before completing the study, the reason for withdrawal must be entered on the appropriate case report form (CRF) page.

## **4 TREATMENTS**

All protocol-specified investigational and non-investigational products are considered study drug.

### **4.1 Study Treatments**

Study drug therapy will be divided into induction and maintenance phases. For the purpose of managing study visits and procedures, a treatment cycle will be defined as 42 days during the induction phase, and as 84 days during the maintenance phase.

#### **4.1.1 Investigational Product**

The investigational product should be stored in a secure area according to local regulations. It is the responsibility of the investigator to ensure that investigational product is only dispensed to study subjects. The investigational product must be dispensed only from official study sites by authorized personnel according to local regulations. In this protocol, investigational product(s) is/are: Panobinostat 5 mg, 10 mg, 15 mg and 20 mg capsules and Ipilimumab.

##### **4.1.1.1 Ipilimumab (BMS-734016)**

Study drug is to be administered and prepared according to the package insert as described below.

#### Preparation of Solution

- Allow the vials to stand at room temperature for approximately 5 minutes prior to preparation of infusion.
- Withdraw the required volume of YERVOY and transfer into an intravenous bag.
- Dilute with 0.9% Sodium Chloride Injection, USP or 5% Dextrose Injection, USP to prepare a diluted solution with a final concentration ranging from 1 mg/mL to 2 mg/mL. Mix diluted solution by gentle inversion.
- Store the diluted solution for no more than 24 hours under refrigeration (2°C to 8°C, 36°F to 46°F) or at room temperature (20°C to 25°C, 68°F to 77°F).
- Discard partially used vials or empty vials of YERVOY.

#### Administration Instructions

- Do not mix YERVOY with, or administer as an infusion with, other medicinal products.
- Flush the intravenous line with 0.9% Sodium Chloride Injection, USP or 5% Dextrose Injection, USP after each dose.
- Administer diluted solution over 90 minutes through an intravenous line containing a sterile, non-pyrogenic, low-protein-binding in-line filter.

#### Dose, Volume and Rate Calculations

Total dose should be calculated as follows:

Subject body weight in kg x 3 mg = total dose, mg

Total infusion volume should be calculated as follows: Total dose in mg divided by 5 mg/mL = infusion volume, mL

Rate of infusion should be calculated as follows: Infusion volume in mL divided by 90 minutes = rate of infusion, mL/min

For example, a subject weighing 114 kg (250 lb) and designated to receive ipilimumab at a dose of 3 mg/kg would be administered 342 mg of ipilimumab (114 kg x 3 mg/kg = 342 mg) with an infusion volume of 70 mL (342 mg divided by 5 mg/mL = 70 mL) at a rate of approximately 0.77 mL/min (70 mL divided by 90 minutes) in 90 minutes.

Ipilimumab (BMS-734016) Injection (5 mg/ml), must be stored refrigerated (2 - 8°C) with protection from light. Ipilimumab may be stored (5 mg/ml) in DEHP free IV infusion bags for up to 24 hours at room temperature or refrigerated (2°C - 8°C). This would include any time in transit and the total time for infusion. Drug must be completely delivered to the subject within 24 hours of preparation.

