De-escalation. The dose escalation plan ([Table 1](#)) follows a simple order restriction, that is, each dose cohort is as high or higher in both doses compared to all lower cohorts. While cohort -1 is below cohort 1, its relative unacceptable toxicity rate is unclear. If de-escalation from cohort 1 is needed, it will go to cohort -1. As long as the decisions are to “stay” at the same dose, cohort -1 will be grown to match that of cohort 1, and then they will be alternated. If for the same number of patients treated, the toxicity differential between them reaches 2, the other cohort will be dropped from further study. It is possible that both cohorts could be considered “the MTD”. In such an event, other features such as patient response would be used to determine which would be the recommended phase 2 dose (RP2D). If the MTD is a unique cohort, that will also be called the RP2D.

This phase I study design has tended to be applied to a fixed sample size of 30. Due to the increased complexity of this combination-dose trial, we have chosen a sample size of 36.

All available clinical and laboratory data, and the nature, time of onset and time to resolution of DLTs observed during dose escalation will be reviewed to determine whether an alternate dose schedule should be examined after consultation between the Investigators and Novartis if needed. If agreed upon, the alternate schedule will be identified by a protocol amendment and the MTD determined for the revised dose schedule.

In addition to the Investigator’s review of study data, the existing Moffitt Protocol Monitoring Committee (PMC) will be utilized to advise on aggregate safety data from this study and more specifically to review all Grade 3 or greater immune-related adverse events (irAEs).

**Dose Limiting Toxicity:** For the purpose of guiding dose escalation decision making, hematologic and non-hematologic (hepatic versus non-hepatic) DLT will be defined separately and will be determined based on the incidence, severity, and duration of study drug-related AEs occurring within 84 days (12 weeks; through Day 42 of induction cycle 2) of initiation of study therapy. For the purposes of subject management, DLTs will lead to dose modification regardless of the cycle in which a DLT occurs (see Section 4.3.6 for specific guidelines).

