**Table 3.1 Dose Escalation regimen for Panobinostat and Ipilimumab**

Dose Cohort	Panobinostat Dose	Ipilimumab Dose
1	5 mg po TIW	3 mg/kg
2	10 mg po TIW	3 mg/kg
3	15 mg po TIW	3 mg/kg
4	20 mg po TIW	3 mg/kg
-1	5 mg po TIW	1 mg/kg

**Dose escalation:** Subjects will be enrolled in successive cohorts of 3. An initial cohort of 3 subjects will be enrolled at the given dose level, and additional cohorts of 3 subjects may be added to the same dose level (e.g. increasing the total number of enrolled subjects from 3 to 6, 9 or 12) based on a modified version of a toxicity probability interval (TPI) design introduced by Ji et al. The modified TPI (mTPI) design uses Bayes rule in a decision theoretic framework to determine the MTD based on a target toxicity (eg, dose limiting toxicity; DLT) probability  $P_T$ . A fixed number of subjects, 36, will be used during this dose escalation study. As the dose escalation proceeds under this design, the number of subjects enrolled at a given dose level depends on the number of the toxicities observed at that dose such that multiple cohorts of 3 subjects each may be enrolled to enable a dose escalation decision. The MTD is selected at the end of dose escalation as the dose with an observed toxicity rate closest to the pre-specified target toxicity probability  $P_T$ . In this study, an 18% target toxicity ( $P_T$ ) is used. Background rationale as basis for selection of this target toxicity has been previously outlined in Section 1.4.6. Dose escalation will evaluate panobinostat at doses ranging from 5 to 20 mg TIW administered in combination with ipilimumab at a dose of 3 mg/kg. The first cohort will receive panobinostat orally at a dose of 5 mg PO TIW; ipilimumab will be administered IV at a dose of 3 mg/kg. Enrollment of successive cohorts of subjects will proceed with administration of escalating doses of panobinostat in combination with ipilimumab. Additional dose levels of panobinostat beyond the 20 mg PO TIW dose cohort may be added if appropriate based on the safety and tolerability profile of the combination, and after consultation and agreement between Investigators and Novartis. It is expected that all subsequent dose levels of panobinostat will be no more than 33% higher than the preceding dose. If the first dose cohort is demonstrated to have unacceptable toxicity, dose level -1 will be instituted with 5 mg PO TIW of panobinostat and ipilimumab at 1 mg/kg.

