#### **4.3.2 Administration of ipilimumab**

Ipilimumab is to be administered as an IV infusion with a 1.2 µm in-line filter (see current version of Investigator's Brochure), using a volumetric pump, at the 3 mg/kg dose, and at an appropriate rate to complete the infusion in 90 minutes with a 10 cc normal saline flush at the end. Additional details on ipilimumab dose are outlined above in Section 4.1.1.1. Refer to Section 4.3.8.1 regarding management of infusion reactions.

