#### **Panobinostat/Ipilimumab Dose Modification Guidelines for Non-hematologic and Hematologic Events Other Than Infusion Reactions:**

- Patients who experience hepatic non-hematologic DLT irrespective of irAE or any Grade 3 or greater irAE will be removed from study with no further dose reduction.
- For patients who experience a first episode of non-hepatic non-hematologic DLT or a first episode of hematologic DLT, therapy may be reinitiated at the next lowest panobinostat/ipilimumab dose level as specified below in Table 4.3 if the event has resolved to less than or equal to Grade 1 in severity at the time the next cycle is due.
- For patients who experience a second episode of either hematologic or non-hepatic non-hematologic DLT, a second dose reduction may be performed as specified below for the successive cycle if the second dose-limiting event is distinct in nature from the first event and the event has resolved to less than or equal to Grade 1 in severity at the time the next cycle is due.
- In the event of a DLT, successive cycles of therapy may be delayed up to 14 days pending resolution of the toxicity to grade 1 or less in severity. Patients on dose level #1 will not be dose reduced in the event of DLT. Patients on dose level #2 will be allowed a maximum of 1 dose reduction, with the second occurrence of DLT necessitating removal from study.
- Any patient who develops significant irreversible (i.e. more than 2 weeks after the last dose of study drug) organ dysfunction (i.e., Grade IV non-hepatic non-hematologic toxicity) or anaphylaxis considered to be related to study drug will also be removed from study with no further dose reduction.
- All cardiac events should be treated as per the local standard of care and referred to a specialist if clinically indicated. The readings of ECGs will use the Fridericia correction: QTcF. Any final decisions concerning dose modifications or permanently discontinuing the patient from study drug due to QTcF prolongation will be based on the

assessment of the principal investigator. If a patient cannot be dosed due to prolonged QTcF for more than 7 days since last dose, patient should be discontinued from study.

**Table 4.2** Criteria for dosing delays, dose-reductions, and re-initiation of treatment due to study drug-related QTcF abnormalities

ECGs to be performed at specified time point	Abnormality Noted	Dose Modification Guideline - At any time during a cycle of therapy (including intended day of dosing)

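### The only ipilimumab dose formula is fixed at 3 mg per kg, so followed literally it triples the dose assigned to cohort -1

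*Combined protocol and SAP*

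**What the plan says.** Under Dose, Volume and Rate Calculations, Section 4.1.1.1 states the total-dose rule as "Subject body weight in kg x 3 mg = total dose, mg". The volume is that dose divided by 5 mg/mL, and the rate is the volume divided by 90 minutes. The worked example concerns a 114 kg subject "designated to receive ipilimumab at a dose of 3 mg/kg would be administered 342 mg of ipilimumab".

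Section 4.3.2 tells staff to infuse "using a volumetric pump, at the 3 mg/kg dose, and at an appropriate rate to complete the infusion in 90 minutes" and then adds: "Additional details on ipilimumab dose are outlined above in Section 4.1.1.1". Neither section mentions 1 mg/kg, and no 1 mg/kg calculation appears anywhere in the document.

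The dose tables differ. Table 1 (Synopsis), Table 3.1, Table 4.1 and Table 4.3 all list cohort -1 as panobinostat 5 mg with ipilimumab 1 mg/kg. The text of Section 3.1 agrees: if the first cohort is too toxic, "dose level -1 will be instituted with 5 mg PO TIW of panobinostat and ipilimumab at 1 mg/kg". The Synopsis sends any de-escalation from cohort 1 to cohort -1, and the D and DU decisions each enroll three new subjects at the lower dose.

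**The concern.** The sections that staff would use to prepare and give the infusion are both written for 3 mg/kg, and one points to the other. Cohort -1 is the only planned cohort to which that figure does not apply.

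Cohorts 1 and -1 differ only in ipilimumab. A cohort -1 subject dosed from the literal formula would therefore receive the cohort 1 regimen, possibly after it had been declared unsafe under a DU decision. That is first a safety matter.

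It also touches the primary objective. The Synopsis grows cohort -1 to match cohort 1 and then alternates between them; if, at equal numbers treated, "the toxicity differential between them reaches 2, the other cohort will be dropped from further study". For any misdosed subjects that rule would compare a regimen with itself. An MTD or RP2D labelled 1 mg/kg could rest partly on data from 3 mg/kg.

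**Working it through.** **Reproducing the plan's example (Section 4.1.1.1).**

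- Dose: 114 kg × 3 mg/kg = 342 mg, as printed.
- Volume: 342 / 5 = 68.4 mL. The protocol prints 70 mL, which is consistent with rounding.
- Rate: 70 / 90 = 0.778 mL/min, against a printed value of about 0.77. From the unrounded volume, 68.4 / 90 = 0.76 mL/min.

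The example is sound for a 3 mg/kg subject. The fault is the constant multiplier in the general formula.

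**Applying the formula to cohort -1.** The ratio is (weight × 3) / (weight × 1) = 3.0, whatever the weight. Four infusions are planned (Days 1 and 22 of two induction cycles). The 70 kg weight is an assumption for illustration.

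| | Literal formula | Assigned 1 mg/kg |
|---|---|---|
| Dose per infusion, 114 kg | 342 mg | 114 mg |
| Volume at 5 mg/mL, 114 kg | 68.4 mL | 22.8 mL |
| Four infusions, 114 kg | 1368 mg | 456 mg |
| Dose per infusion, 70 kg | 210 mg | 70 mg |

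**How likely cohort -1 is to open.** This is the chance that the first pass through cohort 1 ends in D or DU under Table 3.2. It is not the chance of a dosing error. Let p be the DLT rate in cohort 1, a_k the binomial probability of exactly k DLTs in 3 subjects, and b = a_2 + a_3.

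*Reading A: 0 of 3 escalates at once.* The exits are:

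- at N = 3, two or more DLTs: b
- at N = 6, reached from 1 of 3, three or more in total: a_1·b
- at N = 9, reached from 2 of 6, three or more in total: a_1²·(1 − a_0)
- at N = 12, reached from 2 of 9, four or more in total: a_1²·a_0·b

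At p = 0.18: a_0 = 0.5514, a_1 = 0.3631, b = 0.0855. The sum is 0.0855 + 0.0311 + 0.0591 + 0.0062 = 0.182.

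*Reading B: 0 of 3 is followed by three more subjects and then the N = 6 row.* Section 3.1 asks for at least three additional patients beyond 9 weeks before escalation. This adds a_0·[a_3 + a_2·(1 − a_0) + a_2·a_0·b]. At p = 0.18, a_2 = 0.0797 and a_3 = 0.0058, so the addition is 0.025 and the total is 0.207.

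| Assumed DLT rate in cohort 1 | Reading A | Reading B |
|---|---|---|
| 8.1% (grade 3-4 dose-limiting rate in the 3 mg/kg phase III trial, Section 1.1.1) | 3.2% | 3.6% |
| 18% (the target rate) | 18.2% | 20.7% |
| 31.2% (grade 3 or higher rate at 10 mg/kg, Section 1.4.4) | 48.1% | 54.0% |

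Later returns from cohort 2 to cohort 1 are not counted.

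**The case against.** The strongest reply is that the assigned dose is never in doubt. Section 4.1.1.1 is a preparation section that follows the package insert, whereas dose selection belongs to Section 4.3. Section 4.3.1 directs the reader to Table 4.1, which stands just before Section 4.3.2 and shows 1 mg/kg for cohort -1. The worked example is expressly for a subject designated to 3 mg/kg. Opening cohort -1 is in itself a decision to lower ipilimumab, at a single open-label site, so staff would have to overlook the one feature that distinguishes the cohort. The opening probabilities also say nothing about misdosing, and the 31.2% input is neither a DLT rate nor a 3 mg/kg figure.

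Much of this stands. A reader who starts from the tables will dose correctly, the harm is contingent, and the upper end of the probability range rests on a weak proxy. But the tables assign a dose, while Section 4.1.1.1 tells staff how to calculate it, and that calculation is wrong for one planned cohort. The qualifier in the example limits the example, not the formula above it; if anything, it shows that designated doses were expected to vary. A protocol for the first human use of this combination should not depend on staff overriding its written arithmetic.

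**Conclusion.** The concern holds. The dosing text and the dose tables conflict for subjects newly enrolled in cohort -1, and the literal formula overdoses them threefold per infusion at every weight. The threefold ratio needs no assumption. How often it could matter depends on cohort -1 opening, which is roughly one chance in five at the 18% target rate and ranges from about 3% to 54% over the assumed DLT rates, and then on someone applying the formula as written, for which the documents give no probability.

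The conclusion does not rely on dose reductions from cohort 1. There the protocol conflicts with itself separately: Section 4.3.6 says "Patients on dose level #1 will not be dose reduced in the event of DLT", yet Table 4.3 lists 1 mg/kg as the first modification for that cohort.

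**What to change.** Make two wording changes in one amendment, before cohort -1 can open:

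- **Section 4.1.1.1:** body weight (kg) × assigned ipilimumab dose (3 or 1 mg/kg) = total dose (mg). A second worked example at 1 mg/kg would help: 114 kg gives 114 mg, or 22.8 mL.
- **Section 4.3.2:** replace the fixed 3 mg/kg with the assigned dose.

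Settle separately whether a cohort 1 patient may be reduced to 1 mg/kg; the revised formula is correct either way. The cost is the amendment itself. Sample size, decision rules and analyses do not change.
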